APPENDIX 3. STATISTICAL MODEL SPECIFICATIONS

MIXED MODEL FOR REPEATED MEASURES (MMRM)

Ods graphics on;

```
PROC MIXED DATA=XXX plots=(studentpanel(marginal) pearsonpanel(marginal));
```

```
  CLASS SUBJID REGION TRTPN WEEK;  
  MODEL TOTCFB = TOTBL REGION TRTPN WEEK TRTPN*WEEK / DDFM=KR RESIDUAL OUTPM=OUTRESIDUAL;  
  REPEATED WEEK/TYPE=UN SUBJECT=SUBJID;  
  LSMEANS TRTPN*WEEK /PDIFF CL;
```

RUN;

*Where WEEK = Week 1, Week 2, Week 4, Week 6;

Ods graphics off;

In case the MMRM model assuming the unstructured covariance variance structure fails to converge, the spatial exponential or spatial power covariance structure will be assumed sequentially along with a robust sandwich estimator. The first covariance structure to yield convergence will be used in the analysis.

```
PROC MIXED EMPIRICAL;
```

```
  CLASS SUBJID REGION TRTPN WEEK;  
  MODEL TOTCFB = TOTBL REGION TRTPN WEEK TRTPN*WEEK / RESIDUAL OUTP=OUTRESIDUAL;  
  REPEATED WEEK/TYPE=SP(EXP) (WEEK) SUBJECT=SUBJID;  
  REPEATED WEEK/TYPE=SP(POW) (WEEK) SUBJECT=SUBJID;  
  LSMEANS TRTPN*WEEK /PDIFF CL COV;
```

RUN;

*EMPIRICAL IS FOR THE SANDWICH ESTIMATOR;

Within-group effect size will be calculated as the absolute value of LS mean of change from baseline divided by SD, obtained as the SE of the LS Mean multiplied by the square root of the treatment group change from baseline sample size at each visit. Between-group effect size at a visit will be calculated as the absolute value of the LS means difference from Placebo divided by the model estimate of the pooled SD at the visit, which is obtained from the square root of the diagonal element, associated at the visit, from the covariance matrix (R matrix of subjects with MADRS total score at all visits). Although the variance-covariance estimates are calculated differently depending on the covariance structure being applied for the model, the diagonal of the R matrix will contain the variance estimate at each visit that can be used for the effect size calculations regardless of the covariance structure.

Document:

Author:

Version Number:

V2.0

Version Date:

21MAY2020

Template No: CS_TP_BS016 Revision 4
Effective Date: 01Apr2016

Reference: CS_WI_BS005

For All SEP-4199 column for safety questionnaires:

- LS Means estimate, 95%CI and SE is obtained using following statements:

```
LSMESTIMATE TRT01PN*AVISITN "MEAN(200MG+400MG) at Week 1" [1, 1 1] [1, 2 1] / CL divisor=2;  
LSMESTIMATE TRT01PN*AVISITN "MEAN(200MG+400MG) at Week 2" [1, 1 2] [1, 2 2] / CL divisor=2;  
LSMESTIMATE TRT01PN*AVISITN "MEAN(200MG+400MG) at Week 4" [1, 1 3] [1, 2 3] / CL divisor=2;  
LSMESTIMATE TRT01PN*AVISITN "MEAN(200MG+400MG) at Week 6" [1, 1 4] [1, 2 4] / CL divisor=2;
```

- LS Means Difference estimate (vs Placebo), 95%CI and SE is obtained using following statements:

```
LSMESTIMATE TRT01PN*AVISITN "MEAN(200MG+400MG) vs Placebo at Week 1" [0.5, 1 1] [0.5, 2 1] [-1, 3 1] / CL ;  
LSMESTIMATE TRT01PN*AVISITN "MEAN(200MG+400MG) vs Placebo at Week 2" [0.5, 1 2] [0.5, 2 2] [-1, 3 2] / CL ;  
LSMESTIMATE TRT01PN*AVISITN "MEAN(200MG+400MG) vs Placebo at Week 4" [0.5, 1 3] [0.5, 2 3] [-1, 3 3] / CL ;  
LSMESTIMATE TRT01PN*AVISITN "MEAN(200MG+400MG) vs Placebo at Week 6" [0.5, 1 4] [0.5, 2 4] [-1, 3 4] / CL ;
```

NORMALITY CHECK

```
PROC UNIVARIATE DATA=OUTRESIDUAL NORMAL;  
    VAR STUDENTRESID;  
    VAR PEARSONRESID;  
RUN;
```

ANALYSIS OF COVARIANCE (ANCOVA)

```
PROC MIXED;  
    BY WEEK;  
    CLASS TRTPN REGION;  
    MODEL TOTCFB = TRTPN REGION TOTBL;  
    LSMEANS TRTPN / PDIFF CL;  
RUN;
```

For All SEP-4199 column for safety questionnaires:

- LS Means estimate, 95%CI and SE is obtained using
LSMESTIMATE TRT01AN "MEAN(200 mg,400mg)" 1 1 0 / CL DIVISOR=2;
- LS Means Difference estimate (versus Placebo) , 95%CI and SE is obtained using
ESTIMATE "MEAN(200+400) VS PLACEBO" TRT01AN 0.5 0.5 -1 / CL;

Document:

Author:

Version Number:
Version Date:

V2.0
21MAY2020

Template No: CS_TP_BS016 Revision 4
Effective Date: 01Apr2016

Reference: CS_WI_BS005

MH TEST (FOR SELECTED SAFETY PARAMETERS)

*Conducted for each separate SEP-4199 group versus Placebo;

```
PROC RANK OUT=OUT1 NPLUS1 TIES=MEAN;  
  VAR VSCFB VSBASE;  
  RANKS RKVSCFB RKVSBASE;  
RUN;
```

```
PROC GLM DATA=OUT1;  
  CLASS TRTPN;  
  MODEL RKVSCFB = TRTPN RKVSBASE;  
  OUTPUT OUT=RESIDUAL R=RESID;  
RUN;
```

```
PROC FREQ DATA=RESIDUAL;  
  TABLES TRTAN*RESID / NOPRINT CMH2;  
RUN;
```

For All SEP-4199 column, please select all data and create a new treatment code equal to 1 if subject was treated by SEP-4199 (either 200mg or 400mg) and equal to 0 if he received Placebo. Then use same code as above with this new treatment code.

TIME TO RESPONSE ANALYSIS

* Select Raw Log-rank p-value in SURVDIFF ods dataset;

* Response probability are obtained in PRODUCTLIMITESTIMATES ods dataset;

```
ODS OUTPUT SURVDIFF=SURVDIFF PRODUCTLIMITESTIMATES=PRODUCTLIMITESTIMATES;  
PROC LIFETEST OUTSURV=PROBRESPONSE TIMELIST=(9 16 30 44);  
  TIME RSPTIME*RSPSTAT(1);  
  STRATA TRTPN / DIFF=CONTROL ('Placebo');  
RUN;
```

```
ODS OUTPUT HAZARDRATIOS=HAZARDRATIOS PARAMETERESTIMATES=PARAMETERESTIMATES;PROC PHREG;  
  CLASS REGION TRTP (REF='Placebo') / PARAM=REF;  
  MODEL RSPTIME*RSPSTAT(1)=TRTP REGION TOTBL;  
  HAZARDRATIO TRTP / DIFF=REF;  
  CONTRAST '200 MG VS. PLACEBO' TRTP 1 0 / ESTIMATE;  
  CONTRAST '400 MG VS. PLACEBO' TRTP 0 1 / ESTIMATE;  
RUN;
```

Document:

Author:

Version Number:

V2.0

Version Date:

21MAY2020

Template No: CS_TP_BS016 Revision 4
Effective Date: 01Apr2016

Reference: CS_WI_BS005

LOGISTIC REGRESSION

* Placebo is reference;
PROC LOGISTIC DESCENDING;
 CLASS TRTPN REGION / PARAM=REF;
 MODEL RESP = TRTPN REGION TOTBL;
 CONTRAST '200 MG vs. PLACEBO' TRTPN 1 0 / ESTIMATE=EXP;
 CONTRAST '400 MG vs. PLACEBO' TRTPN 0 1 / ESTIMATE=EXP;
 CONTRAST '200 MG vs. 400 MG' TRTPN -1 1 / ESTIMATE=EXP;
CONTRAST '(200 MG + 400 MG) vs Placebo' TRTPN 0.5 0.5 / ESTIMATE=EXP;RUN;

COCHRAN-ARMITAGE TEST

```
PROC FREQ;  
    TABLE TRTP*RESP/CMH TREND;  
RUN;
```

MULTIPLICITY-ADJUSTED P-VALUES

*Example raw p-values;
DATA STUDY;
 INPUT HYP \$ FAMILY PARALLEL \$ SERIAL \$ RAWP;
 DATALINES;
 H1 1 0000 0000 0.1403
 H2 1 0000 0000 0.0095
 H3 2 0000 1000 0.0559
 H4 2 0000 0100 0.0051
 ;
RUN;

%TREEGATE(TEST=HOCHBERG, GAMMA=0.9);

Document:

Author:

Version Number:
Version Date:

V2.0
21MAY2020

Template No: CS_TP_BS016 Revision 4
Effective Date: 01Apr2016

Reference: CS_WI_BS005

PATTERN MIXTURE MODEL (PMM) WITH PLACEBO BASED MI

The steps to implement this sensitivity analysis are as follows. For Japan cohort analysis, code must be adapted by removing REGION variable.

Step 1: Intermittent missing MADRS total scores will be imputed for each treatment using non-missing data from all ITT subjects within the treatment group by a Markov Chain Monte Carlo (MCMC) imputation model which assumes a multivariate normal distribution over all variables included in the imputation model. This imputation is based on the MAR assumption, ie, the missing data are assumed to follow the same model as the other patients in their respective treatment group.

```
PROC MI DATA=xxx OUT=yyy NIMPUTE=1000 SEED=12345 MINIMUM=. . 0 0 0 0 MAXIMUM=. . 60 60 60 60  
MINMAXITER=100;  
    BY TRTP;  
    VAR REGION MADRS_BASE MADRS_Wk1 MADRS_Wk2 MADRS_Wk4 MADRS_Wk6;  
    MCMC CHAIN=MULTIPLE IMPUTE=MONOTONE NBITER=5000 NITER=200;  
RUN;
```

As a result, each of the 1000 datasets will only have a monotone missing data pattern.

There is no missing value expected at baseline for MADRS total score since it is related to inclusion/exclusion criteria. For the secondary endpoint, there could be missing values at baseline for CGI-BP-S scores. To impute CGI-BP-S scores, intermittent imputation to obtain monotone missing pattern has two steps, 1a and 1b.

In Step 1a, missing baseline CGI-BP-S total scores will be imputed. In Step 1b, the intermittent missing data will be filled in, assuming MAR, to obtain only monotone missing data.

Step 1a: If there are any ITT subjects who do not have a baseline CGI-BP-S total score, their baseline data needs to be imputed first. Missing baseline data will be imputed using a monotone regression on 100 imputations with a model that includes region, and baseline CGI-BP-S depression score. Additional covariates may be added as appropriate.

```
PROC MI DATA=xxx OUT=aaa NIMPUTE=100 SEED=1234 MINIMUM=. 1 MAXIMUM=. 7 MINMAXITER=100;  
    BY TRTP;  
    VAR REGION CGI_BASE;  
    MCMC CHAIN=MULTIPLE IMPUTE=MONOTONE NBITER=5000 NITER=200;  
RUN;
```

Step 1b: Intermittent missing CGI-BP-S total scores will be imputed for each TRTP using non-missing data from all subjects within the treatment group by MCMC imputation model which assumes a multivariate normal distribution over all variables included in the imputation model. This imputation is based on the MAR assumption, ie, the missing data are assumed to follow the same model as the other patients in their respective treatment group.

Document:

Author:

Version Number:

V2.0

Version Date:

21MAY2020

Template No: CS_TP_BS016 Revision 4
Effective Date: 01Apr2016

Reference: CS_WI_BS005

```

PROC MI DATA=aaa OUT=yyy NIMPUTE=10 SEED=4567 MIN=..1111 MAX=..7777 MINMAXITER=100;
    BY _IMPUTATION_;
    BY TRTP;
    VAR REGION CGI_BASE CGI_WK1 CGI_WK2 CGI_WK4 CGI_WK6;
    MCMC CHAIN=MULTIPLE IMPUTE=MONOTONE NBITER=5000 NITER=200;
RUN;

```

As a result, each of the 1000 datasets will only have a monotone missing data pattern.

Step 2: This step will use the MNAR assumption (placebo group based imputation). The assumption is that the trajectories of all the patients (including the placebo group subjects who discontinue) are assumed to follow the placebo group after their discontinuation.

```

PROC MI DATA = yyy OUT = zzz NIMPUTE = 1 SEED = 56789 MINIMUM=..0000 MAXIMUM=..60606060;
    BY _IMPUTATION_;
    VAR REGION MADRS_BASE MADRS_WK1 MADRS_WK2 MADRS_WK4 MADRS_WK6;
    CLASS TRTP REGION;
    MONOTONE REGRESSION(/ DETAILS);
    MNAR MODEL(MADRS_WK1 MADRS_WK2 MADRS_WK4 MADRS_WK6/ MODELOBS = (TRTP = 'Placebo'));
RUN;

```

The MODEL option specifies that only observations where TRT = "Placebo" are used to derive the imputation model for the missing postbaseline MADRS scores. Thus, the TRT variable is not specified in the VAR list. This approach is also known as jump to reference (jump to placebo in our case) where it is assumed that the discontinuations from the SEP-4199 treatment groups immediately change to have the distribution of the placebo group. This imputation model is also the imputation model that is used to impute missing postbaseline observations in the placebo group.

Step 3: Fit the primary MMRM model using each of the 1000 imputed datasets (BY _IMPUTATION_) and calculate the inferential statistics on each imputed dataset.

```

PROC MIXED DATA=zzz;
    BY _IMPUTATION_;
    CLASS SUBJID REGION TRTP WEEK;
    MODEL TOTCFB = MADRS_BASE REGION TRTP WEEK TRTP*WEEK / DDFM=KR;
    REPEATED WEEK/TYPE=UN SUBJECT=SUBJID;
    LSMEANS TRTP*WEEK /PDIFF CL;
    ODS OUTPUT DIFFS=CHGDIFF LSMEANS=CHGLSMN;
RUN;

```

Step 4. Use proc MIANALYZE to combine the estimates from Step 3 based on Rubin's imputation rules. See example for LS Means below.

```

PROC MIANALYZE DATA = CHGLSMN;
    BY TRTP WEEK;
    MODELEFFECTS ESTIMATE;

```

Document:

Author:

Version Number:

V2.0

Version Date:

21MAY2020

Template No: CS_TP_BS016 Revision 4
 Effective Date: 01Apr2016

Reference: CS_WI_BS005

```
STDERR STDERR;  
ODS OUTPUT PARAMETERESTIMATES = LSMN (DROP = PARM);  
RUN;
```

TIPPING POINT ANALYSIS

This analysis assumes that the data in the SEP-4199 treatment groups is not missing at random. The tipping point based assumption will be used, ie, the trajectories of the subjects in the SEP-4199 treatment groups after withdrawal are assumed to be worse by an amount of delta, after the MI using the MAR assumption.

The steps to implement this sensitivity analysis are as follows. For Japan cohort analysis, code must be adapted by removing REGION variable.

Step 1: Run the primary MMRM analysis for the ITT population. Obtain LS mean difference between each SEP-4199 group and the placebo group at each visit. Suppose these values are stored in variable LSMDIFF in dataset DIFF (LSMDIFF_200_PLACEBO, LSMDIFF_400_PLACEBO). This dataset should also contain the variable WEEK. These differences will be used when applying penalty on the imputed values.

Step 2: Similar to above, intermittent missing data will be filled in, assuming MAR, to obtain only monotone missing data.

```
PROC MI DATA=xxx OUT=yyy NIMPUTE=1000 SEED=12345 MINIMUM=. . 0 0 0 0 MAXIMUM=. . 60 60 60 60  
MINMAXITER=100;  
BY TRTP;  
VAR REGION MADRS_BASE MADRS_Wk1 MADRS_Wk2 MADRS_Wk4 MADRS_Wk6;  
MCMC CHAIN=MULTIPLE IMPUTE=MONOTONE NBITER=5000 NITER=200;  
RUN;
```

Step 3: Impute the remaining missing data using an MAR-based regression model.

```
PROC MI DATA = yyy OUT = zzz NIMPUTE = 1 SEED = 56789 MINIMUM= . . 0 0 0 0 MAXIMUM= . . 60 60 60 60  
MINMAXITER=100;  
BY _IMPUTATION_;  
VAR TRTP REGION MADRS_BASE MADRS_WK1 MADRS_WK2 MADRS_WK4 MADRS_WK6;  
CLASS TRTP REGION;  
MONOTONE REGRESSION;  
RUN;
```

Step 4: For a range of penalty values (ie, 5%, 10%, etc of the LS mean difference obtained in Step 1), apply penalty to the change from baseline values calculated from imputed MADRS total scores in each SEP-4199 group at each postbaseline visit.

Suppose ANALYSIS is the dataset reformatted from zzz that contains each subject's data in long format. It should contain the missing value flag MISSVAL (ie, whether the MADRS total score for a given visit is missing in the original data): 1 = missing; 0 = available. Other variables in analysis should

Document:

Author:

Version Number:

V2.0

Version Date:

21MAY2020

Template No: CS_TP_BS016 Revision 4
Effective Date: 01Apr2016

Reference: CS_WI_BS005

include: SUBJID, TRTP, REGION, WEEK, TOTBL, AVAL (MADRS total score at each postbaseline visit), TOTCFB, LSMDIFF, and _IMPUTATION_.

```
DATA ANALYSIS_PENALTY;
  SET ANALYSIS;
  /* store the original TOTCFB values in ORIGCHG */
  ORIGCHG = TOTCFB;
  /* if a MADRS total score is missing in the original dataset, apply a penalty to the TOTCFB value in each SEP-4199 group only */
  DELTA = XXX;
  IF MISSVAL=1 AND TRTP="200 MG" THEN TOTCFB = ORIGCHG - ((DELTA/100)* LSMDIFF_200_PLACEBO);
  IF MISSVAL=1 AND TRTP="400 MG" THEN TOTCFB = ORIGCHG - ((DELTA/100)* LSMDIFF_400_PLACEBO);
RUN;
```

Repeat the above step for all delta values, ie, 5, 10, ..., 100%.

Step 5: Fit the primary MMRM model for each penalty and imputation to obtain the estimates at each postbaseline visit.

Suppose the primary MMRM model adopted the unstructured covariance model:

```
ODS OUTPUT DIFFS=CHGDIFF_TIPPING LSMEANS=CHGLSMN_TIPPING;
PROC MIXED DATA=ANALYSIS_PENALTY;
  BY DELTA _IMPUTATION_;
  CLASS SUBJID REGION TRTP WEEK;
  MODEL TOTCFB = TOTBL REGION TRTP WEEK TRTP*WEEK / DDFM=KR;
  REPEATED WEEK / SUB=SUBJID TYPE=UN;
  LSMEANS TRTP*WEEK / PDIFF CL;
RUN;
```

Step 6: Use proc MIANALYZE similar to above to combine the estimates from each imputation for each delta using Rubin's rules. See example for LS Means below.

```
ODS OUTPUT PARAMETERESTIMATES=LSMEST_TIPPING_MIAN;
PROC MIANALYZE DATA = CHGLSMN_TIPPING;
  BY DELTA TRTP WEEK;
  MODELEFFECTS ESTIMATE;
  STDERR STDERR;
RUN;
```

This analysis is repeated for a range of deltas, starting at 0% of the treatment difference at each postbaseline visit, and increasing in increments of 5% until either the tipping point (where the statistical significance of the treatment effect is lost) is identified or the 100% penalty is applied. Tipping point could be reached at different deltas for each SEP-4199 treatment group. Once the tipping point %delta is identified, smaller %delta increments (eg 1%) may be selected for further analysis.

Document:

Author:

Version Number:
Version Date:

V2.0

21MAY2020

Template No: CS_TP_BS016 Revision 4
Effective Date: 01Apr2016

Reference: CS_WI_BS005

MCP-MOD ANALYSIS

The primary efficacy endpoint, change from baseline in MADRS score at Week 6, will also be analyzed using the gMCP-Mod approach for the ITT population. The analysis will be done in two steps.

Step 1: MCP step

The MCP step consists of specifying a set of candidate models for the dose response relationship. First, the following four candidate model families will be selected to describe the potential dose-response curve $f(d, \theta)$.

- Linear model: $f(d, \theta) = E_0 + \delta d$

For the linear model, E_0 is the drug effect at $d \approx 0$ and δ is the slope associated with d . There is no parameter to be estimated for the linear model.

- Quadratic model: $f(d, \theta) = d + \delta d^2$

The quadratic model is intended to capture a possible non-monotonic dose-response relationship. For the quadratic model, there is one parameter δ to be estimated.

- E_{\max} model: $f(d, \theta) = E_0 + E_{\max} d / (ED_{50} + d)$

The E_{\max} model is used to represent monotone, concave dose-response shapes. To distinguish it from the more general sigmoid E_{\max} model it is sometimes also called hyperbolic E_{\max} model. For the E_{\max} model, there is one parameter ED_{50} to be estimated.

- Sigmoidal E_{\max} : $f(d, \theta) = E_0 + E_{\max} d^h / (ED_{50}^h + d^h)$

The sigmoid E_{\max} model is an extension of the (hyperbolic) E_{\max} model by introducing an additional parameter h , that determines the steepness of the curve at the ED_{50} value. The sigmoid E_{\max} model describes monotonic, sigmoid dose-response relationships. For the Sigmoid E_{\max} model, there are two parameters ED_{50} and h to be estimated.

The next step is to determine the initial values of model parameters for the candidate models. Initial values for standardized model parameters can be calculated based on observed value at Week 6..

```
fitlinear<- fitMod(dose=dose, resp= resp, data = xxx, model="linear")
fitquadratic<- fitMod(dose=dose, resp= resp, data = xxx, model="quadratic")
fitemax<- fitMod(dose=dose, resp=resp, data = xxx, model="emax")
fitsigemax<- fitMod(dose=dose, resp=resp, data = xxx, model="sigEmax")
```

Note: Dose is 0 for placebo, 200 for SEP-4199 200mg/day and 400 for SEP-4199 400mg/day. Resp is the response so change from baseline at Week 6 in MADRS Total Score.

Document:

Author:

Version Number:

V2.0

Version Date:

21MAY2020

Template No: CS_TP_BS016 Revision 4
Effective Date: 01Apr2016

Reference: CS_WI_BS005

Based on an estimate of the dose-response vector and its associate variance/covariance matrix, optimal contrast will be computed for each model to maximize the power to test the null hypothesis of a constant dose-response curve. To obtain this estimate, an MMRM model with factors for treatment dose level, region, week, and baseline MADRS score as a continuous covariate will be used to model the change from baseline in MADRS score over time from the placebo and SEP-4199 groups for the ITT population. This analysis can be performed using the SAS software ([Dmitrienko, 2017](#)).

```

PROC MIXED;
  CLASS SUBJID REGION TRTPN WEEK;
  MODEL TOTCFB = TOTBL REGION TRTPN WEEK TRTP*WEEK / DDFM=KR RESIDUAL;
  REPEATED WEEK/TYPE=UN SUBJECT=SUBJID;
  LSMEANS TRTPN*WEEK /PDIFF CL COV;
  *ODS OUTPUT LSMEANS=MUH (KEEP=TRTPN WEEK ESTIMATE);
  *ODS OUTPUT LSMEANS=COVH (KEEP=TRTPN WEEK COVx COVy COVz) ;
RUN;

```

where COVx COVy COVz are representing the columns associated to LS Means estimated for Placebo, SEP-4199 200mg/day and 400 for SEP-4199 400mg/day at Week 6.

The vector of the optimal contrast estimates corresponding to the set of candidate models is asymptotically normally distributed. The test statistic used for establishing an overall dose response signal is the maximum t-statistics of the individual model test statistics. Critical values for tests with (asymptotically) exact level α can be derived from the joint distribution of the t statistics, which can be obtained from the joint distribution of the contrast estimates ([Pinheiro 2014](#)). Multiplicity adjusted p-values for the individual model contrast tests can be derived similarly. The mvtnorm package in R includes functions to calculate quantiles and probabilities for the underlying multivariate normal distributions ([Pinheiro 2014](#), [Genz 2009](#)).

The optimal contrasts corresponding to the candidate models are calculated using the optContr function in the DoseFinding package in R ([Pinheiro 2014](#)). Model specific contrast coefficients and contrast correlation matrix will be displayed in R outputs.

```

doses <- c(0, 200, 400)
Delta=coef(fitquadratic)[["b2"]]/abs(coef(fitquadratic)[["b1"]])

mod <- Mods(emax = coef(fitemax)[["ed50"]],
            quadratic = Delta,
            sigEmax = coef(fitsigemax)[c("ed50","h")],
            linear = NULL,
            doses = doses, direction = "decreasing")
plot(mod, xlab= "Doses" , ylab= "Model Means" )

contMat <- optContr(mod, S=covH)
summary(contMat)
plot(contMat, xlab= "Doses" , ylab= "Optimal Contrasts" )

```

Document:

Author:

Version Number:
Version Date:

V2.0
21MAY2020

Template No: CS_TP_BS016 Revision 4
Effective Date: 01Apr2016

Reference: CS_WI_BS005

The optimal model contrast tests will be performed using the MCTtest function in the DoseFinding package in R, based on the multiple comparison approach described above (Pinheiro 2014).

```
MCTtest(doses, muH, S=covH, type = "general", critV = TRUE, pVal = TRUE, alpha=0.05, alternative='one.sided', contMat=contMat)
```

Step 2: Mod step

After a dose response signal is established in the first step, one proceeds to the Mod step, fitting the dose response profile and estimating target doses based on the models identified in the MCP step (Pinheiro 2014). The candidate models will be retained to fit the data. The Generalized AIC (gAIC) will be used to select the model for which the maximum likelihood fit provides the smallest gAIC value. The fitMod function in DoseFinding can be used for this analysis.

If at least one significant model is found in Step 1 then use following code:

```
ModStep=MCPMod(doses, muH, S=covH, models=mod, type = "general", doseType="TD", Delta=3.5, pVal = T)
```

If no significant model is found in Step 1 then use following code:

```
ModStepEM <- fitMod(doses, muH, S=covH, model="emax", type = "general")
gAIC(ModStepEM)
coef(ModStepEM)
plot(ModStepEM)
```

```
ModStepQ <- fitMod(doses, muH, S=covH, model="quadratic", type = "general")
gAIC(ModStepQ)
coef(ModStepQ)
plot(ModStepQ)
```

```
ModStepLin <- fitMod(doses, muH, S=covH, model="linear", type = "general")
gAIC(ModStepLin)
coef(ModStepLin)
plot(ModStepLin)
```

```
ModStepsigEM <- fitMod(doses, muH, S=covH, model="sigEmax", type = "general")
gAIC(ModStepsigEM)
coef(ModStepsigEM)
plot(ModStepsigEM)
```

Document:

Author:

Version Number:
Version Date:

V2.0
21MAY2020

Template No: CS_TP_BS016 Revision 4
Effective Date: 01Apr2016

Reference: CS_WI_BS005

Estimation of target doses is done based on the selected fitted model for the dose response parameter ([Bornkamp 2009](#)).

TD(ModStep, Delta=xxx, direction="decreasing")

TD(ModStep, Delta=xxx, TDtype = "discrete", doses=doses, direction="decreasing")

Note: Appropriate Delta will be explored based on results

ED(ModStep, p=0.5)

ED(ModStep, p=0.5, EDtype = "discrete", doses=doses)

Note: Repeat for 10%, 25%, 50%, 75% and 90%

Alternatively, model averaging approaches can be used to avoid the need to select a single model. The individual AIC values for the candidate models with significant contrast test statistics determine the model averaging weights ([Buckland 1997](#)). This applies both to dose response and target dose estimation ([Pinheiro 2014](#)).

MM2 <- MCPMod(doses, muH, S=covH, type = "general", models=mod, alpha = 0.05, Delta=xxx, selModel = "aveAIC", doseType = "TD", alternative = "one.sided")

Note: Appropriate Delta will be explored based on results

TDEst <- MM2\$doseEst%*%MM2\$selMod

TDEst

PK ANALYSIS

If there is at least one PK concentration <LLOQ within a treatment group at a time point, two approaches will be used to handle the BLQ data. The first approach is to set PK concentration < LLOQ to $\frac{1}{2}$ LLOQ for summary statistics calculations.

A second approach is to assume a truncated normal distribution for the specific concentration data if at least 10% of the concentrations at a time point are <LLOQ within a treatment group. The likelihood of the BLQ sample assumes that the value is less than the LLOQ, and the BLQ data will be censored with values less than LLOQ as LLOQ. Proc Lifereg in SAS will be used to perform a Tobit analysis. The Tobit model is a regression model for left-censored data assuming a normally distributed error term. The model parameters are estimated by maximum likelihood. Mean and SD will be provided by visit and treatment group.

```
DATA XXX;  
  SET XXX;  
  IF AVAL<AAA THEN DO;  
    LOWER=.;  
    UPPER=AAA;  
  END;  
  ELSE DO;
```

Document:

Author:

Version Number:

V2.0

Version Date:

21MAY2020

Template No: CS_TP_BS016 Revision 4
Effective Date: 01Apr2016

Reference: CS_WI_BS005

```
LOWER=AVAL; UPPER=AVAL;  
END;  
RUN;  
  
PROC LIFEREG DATA=XXX;  
  BY TRT01A WEEK;  
  MODEL (LOWER, UPPER) = / D=NORMAL;  
RUN;
```

Document:

Author:

Version Number:

V2.0

Version Date:

21MAY2020

Template No: CS_TP_BS016 Revision 4
Effective Date: 01Apr2016

Reference: CS_WI_BS005

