15.3.6.3. Clinical Laboratory Assessments

All summaries involving clinical chemistry, hematology, and urinalysis tests will be based on the Safety population.

Descriptive statistics for absolute value and change from baseline will be displayed at each visit by treatment group for each chemistry, hematology, and urinalysis laboratory test measured on a continuous scale. Serum prolactin values will be summarized by treatment group and gender.

Nonparametric rank ANCOVA with adjustments for baseline value will be applied to change from baseline in serum prolactin, lipids, glucose, for comparison between each SEP-4199 group and placebo. Serum prolactin will be assessed separately by gender.

The normal reference ranges for laboratory tests will be used to determine whether the laboratory test value is below, within, or above the normal range. Shifts from baseline will be produced by treatment group to show the percentage of subjects with laboratory test values below, within, and above the normal range.

The number and percentage of subjects with a Markedly Abnormal Post-baseline Laboratory value (MAPLV, to be defined in the SAP) for select parameters will be summarized by post-baseline visit and overall for each treatment group.

The data listings for laboratory parameters will flag values outside of the reference range.

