- Serum prolactin results will be summarized overall and separately by gender. Glucose, insulin, and lipid panel results, along with a derived variable for homeostasis model assessment of insulin resistance (HOMA-IR) will be summarized for fasting only and overall (fasting, non-fasting, or fasting status unknown combined) status. HOMA-IR will be derived based on glucose and insulin results as: $HOMA-IR = \text{Glucose (mg/dL)} \times \text{Insulin (mU/L)} / 405$ ([Matthews 1985](#)). HbA1c will also be summarized.
- The change from baseline values at Week 6 for selected laboratory parameters will be evaluated using a nonparametric rank ANCOVA analysis with adjustments for the corresponding baseline values for comparison between each SEP-4199 group and placebo. Using the regression residuals from the rank ANCOVA analysis as scores, the Mantel-Haenszel row mean scores test will be used to compare between the treatment groups. This analysis will be conducted for CRP, Glucose (Fasting and Overall), Insulin (Fasting and Overall), HOMA-IR (Fasting and Overall), Cholesterol Total (Fasting and overall), HDL (Fasting and Overall), LDL (Fasting and Overall), Triglycerides (Fasting and Overall), Prolactin (Overall, Male, and Female), and HbA1c (Fraction of 1).

All laboratory data will be provided in data listings, with the values outside the reference ranges flagged.

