18.1. DERIVATION

LLOQ is 0.0500 ng/mL for R-amisulpride and S-amisulpride and LLOQ is 1.56 ng/mL for plasma prolactin.

Below derivations apply after concentrations lower than LLOQ are set to $\frac{1}{2}$ LLOQ.

- Coefficient of variation
$$100 * \text{Standard Deviation} / \text{Mean}$$
- Geometric Mean
$$\text{Exponential}(\text{mean of } \log_e \text{ transformed data})$$
- Geometric CV
$$\text{Square Root}(\text{Exponential}(\text{Variance}(\log_e \text{ transformed data}) - 1)) * 100$$

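### The SAP's rank-ANCOVA code removes the treatment effect before testing for it, so the planned prolactin, metabolic and weight comparisons give p = 1 whatever the data; the geometric-CV formula is also misprinted

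*SAP*

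**What the plan says.** Protocol Section 15.3.6.3 states: "Nonparametric rank ANCOVA with adjustments for baseline value will be applied to change from baseline in serum prolactin, lipids, glucose", comparing each SEP-4199 group with placebo. Section 15.3.6.5 promises the same for weight and BMI.

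SAP Section 17.2 turns this into a two-step procedure: "Using the regression residuals from the rank ANCOVA analysis as scores, the Mantel-Haenszel row mean scores test will be used" to compare the groups. It lists CRP, glucose, insulin, HOMA-IR, total cholesterol, HDL, LDL, triglycerides, prolactin (overall and by sex) and HbA1c. Section 17.4 applies the same test to vital signs, a list that includes weight and BMI.

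The code is in SAP Appendix 3 under the MH test heading, marked "Conducted for each separate SEP-4199 group versus Placebo":

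- ranks: "PROC RANK OUT=OUT1 NPLUS1 TIES=MEAN"
- regression: "MODEL RKVSCFB = TRTPN RKVSBASE", with TRTPN as a class variable
- scores: "OUTPUT OUT=RESIDUAL R=RESID"
- test: "TABLES TRTAN*RESID / NOPRINT CMH2"

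The pooled All SEP-4199 comparison reuses this code with a new treatment indicator.

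SAP Section 18.1 defines the geometric CV of the concentration data as the square root of the exponential of (log-scale variance minus 1), times 100. The subtraction is inside the exponential.

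**The concern.** The residual method works by regressing the rank of change on the rank of baseline alone. What is left over still contains any treatment effect, and the Mantel-Haenszel step tests it. Once treatment is also in the regression, its effect has been fitted and subtracted, and the second step has nothing to find.

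SAP Section 17 makes no between-group safety comparisons unless a section specifies one. For the parameters listed in Section 17.2, and for weight and BMI, this is the only one specified. Prolactin matters most: Protocol Section 7.3.1 describes the S-enantiomer as a D2 antagonist, and Section 7.2.2 keeps prolactin blinded after screening. Run as written, the tables would show p-values of 1.000 that look like evidence of no difference but carry no information.

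The geometric-CV formula is a smaller, descriptive matter. It would misstate the spread wherever a geometric CV is reported for amisulpride enantiomers, total amisulpride or plasma prolactin.

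**Working it through.** The documents give no numerical result for this test, so there is no figure to reproduce. The check is algebra, then simulation.

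**Algebra.** Let e be the residual from regressing the rank of change on an intercept, treatment indicators and the rank of baseline. The normal equations make e orthogonal to every column of the design, including each arm's indicator. So the sum of e within arm k is 0, and each arm mean is 0.

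The row-mean-score statistic for one stratum is

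Q = (n − 1) × Σ n_k (ē_k − ē)² / Σ (e_i − ē)².

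With every ē_k = 0 and ē = 0, the numerator is 0. Hence Q = 0 and p = 1 for any data.

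**Simulation.** The three steps were re-implemented: ranks divided by n + 1 with mean ranks for ties, least squares, and the row-mean-score chi-square.

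- From the documents: 93 per arm (SAP Section 3.4), 15 per arm (Japanese cohort), two-sided 0.05 (SAP Section 6.6).
- Assumed: normal data, baseline slope −0.5, treatment shifts of 0, 0.44, 1 and 3 residual SD.
- 2,000 trials per setting, with planned treatment equal to actual treatment.

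| n per arm | Shift (SD) | Rejections as coded | Smallest p as coded | Rejections with TRTPN deleted |
|---|---|---|---|---|
| 93 | 0 | 0% | 1.000000 | 4.6% |
| 93 | 0.44 | 0% | 1.000000 | 82% |
| 93 | 1 | 0% | 1.000000 | 100% |
| 93 | 3 | 0% | 1.000000 | 100% |
| 15 | 0 | 0% | 1.000000 | 4.2% |
| 15 | 0.44 | 0% | 1.000000 | 18% |
| 15 | 1 | 0% | 1.000000 | 68% |
| 15 | 3 | 0% | 1.000000 | 100% |

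The largest Q from the code as written was about 8 × 10⁻²⁸, which is rounding error. Fitting the regression to all three arms and testing pairwise, or pooling the active arms, gives the same result.

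**Planned versus actual treatment.** The regression uses TRTPN and the test uses TRTAN, so p is exactly 1 only if the two agree for everyone compared. With 1, 2 or 5 of 186 subjects mismatched, median p was about 0.91, 0.88 and 0.82, and the smallest simulated p was 0.65, 0.43 and 0.18. No trial rejected. These values reflect the misclassified subjects and do not measure the treatment effect. SAP Section 5.3 expects the two variables to agree in general.

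**Geometric CV.** With s² the variance of the log data, the lognormal formula is √(exp(s²) − 1) × 100. The SAP prints √(exp(s² − 1)) × 100.

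| s² | Correct | SAP formula |
|---|---|---|
| 0 | 0% | √exp(−1) = 61% |
| 0.04 | √(exp(0.04) − 1) = 20% | √exp(−0.96) = 62% |
| 0.25 | √(exp(0.25) − 1) = 53% | √exp(−0.75) = 69% |
| 1.0 | √(exp(1) − 1) = 131% | √exp(0) = 100% |

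The two agree only where exp(s²)(1 − exp(−1)) = 1, that is s² = 0.459, a geometric CV of about 76%. Below that the SAP formula overstates the spread; above it, the formula understates it. It can never return less than 60.65%.

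**The case against.** The strongest reply is that the code already contains a valid test. The PROC GLM step is a rank ANCOVA, and its adjusted F-test for treatment performs like the repaired residual test: in simulation at 93 per arm and a 0.5 SD shift, 92.2% against 92.1% rejections. The protocol's named method is therefore fitted. But SAP Section 17.2 names the Mantel-Haenszel result as the comparison, and nothing in the SAP reports the F-test. The planned p-value is the empty one.

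Second, these are safety comparisons outside the multiplicity plan, and the same parameters are also summarised by arm, with reference-range shifts and markedly abnormal counts for the laboratory tests. A large prolactin rise would still be visible, and a column of p = 1.000 beside different means would probably be noticed. The stopping rule for amenorrhea, gynecomastia and galactorrhea acts on adverse events and does not depend on this test. All of that stands and limits the harm, but it does not make the specified test work.

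Third, the power at 93 per arm does not carry over to the sex-specific prolactin tests. At an assumed 45 per arm, the repaired test rejects about 65% at 0.5 SD. That is fair, but the failure of the code does not depend on sample size.

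Fourth, the geometric-CV point rests on bracket placement in an equation read from PDF, and the QTc equations in Section 17.3.1 were visibly affected by that conversion. The brackets in Section 18.1 do balance as printed, with the minus one inside the exponential. The statistic is descriptive and reported only where appropriate, so this part is secondary and should be checked against the source file.

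**Conclusion.** The concern holds. As coded, the Mantel-Haenszel comparison cannot detect any treatment difference in the listed laboratory parameters, weight or BMI, for either dose or the pooled drug group. With planned and actual treatment equal, p = 1 is an algebraic identity and needs no distributional assumption. With a few mismatches, p is arbitrary, and none of the simulated trials reached significance. The power of the repaired test does rest on the assumed data model and shifts.

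The defect lies in the Appendix 3 code; the text of Section 17.2 can be read as the standard baseline-only method. Primary and secondary efficacy tests, power and type I error are untouched. The geometric-CV formula is also wrong as printed, from 61% instead of 0% at zero variance to 100% instead of 131% at log-variance 1. It is the lesser of the two errors.

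**What to change.** 1. In SAP Appendix 3, change the regression to `MODEL RKVSCFB = RKVSBASE` by deleting TRTPN, and pass those residuals to the Mantel-Haenszel step. Apply the same change to the pooled All SEP-4199 run.
2. Use one treatment variable throughout this block: actual treatment (TRTAN), consistent with the Safety population definition.
3. In SAP Section 17.2, say explicitly that the residual-generating regression contains baseline rank only.
4. In SAP Section 18.1, move the bracket so that the formula reads Square Root(Exponential(Variance of log data) − 1) × 100, after checking the source file.

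The cost is a few lines of text and code. No data collection, sample size or efficacy analysis changes. The correction should be documented before the code is run on unblinded data; made later, it becomes a deviation that SAP Section 20 requires to be described and justified in the final report.
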